3.1.1.2 Non-Hematologic exceptions

- Transient (< 24 hours) grade 3 hypoalbuminemia, hypokalemia, hypomagnesemia, hyponatremia or hypophosphatemia which responds to medical intervention. rhIL-15 and avelumab will be continued while the metabolic abnormalities are corrected by intravenous or oral supplementation
- Non-sustained (< 7 days) grade 3 liver function test (ATL, AST, alkaline phosphatase, total or direct bilirubin) abnormalities deemed unrelated or unlikely related to avelumab, in the absence of clinical signs of hepatic dysfunction (lethargy, confusion, anorexia, pruritus, tremor); for patients with baseline grade 1 elevations, any increase $\geq 10 \times$ baseline will be considered dose-limiting and these patients will be closely monitored for liver function abnormalities. rhIL-15 and avelumab will be continued as long as these abnormalities do not persist for more than 7 days or the patient does not exhibit findings consistent with hepatic toxicity

Management and dose modifications associated with the above adverse events are outlined in Section 3.3. Occurrence of any DLT-defining toxicity after the first 28 days of treatment will lead to permanent discontinuation of protocol therapy; however, will not be deemed a DLT for purposes of dose escalation.

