3 STUDY IMPLEMENTATION

3.1 STUDY DESIGN

In patients with relapsed or refractory T-cell malignancies, IL-15 will be administered by continuous intravenous infusion in a dose-escalation 3 + 3 system with a starting dose of 1 mcg/kg/day, a second dose level of 2 mcg/kg/day, a third dose level at 3 mcg/kg/day, and a fourth dose level at 4 mcg/kg/day on days 1-5 of each of six cycles. Avelumab (IV over 1 hour) will be administered at a dose of 10 mg/kg on days 8 and 22 of the cycle. Treatment will continue for a maximum of 6 cycles or until toxicity (i.e., dose limiting toxicity as found in Section 3.1.1 or toxicity requiring hold as defined in Section 3.3) or progressive disease.

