3.8.1 Criteria for removal from protocol therapy

Patients who meet the following criteria should be discontinued from protocol therapy:

- Completion of protocol therapy (i.e., up to 6 cycles)
- Confirmed disease progression
- Intercurrent illness that prevents further administration of treatment
- Unacceptable toxicities as listed in Section [3.1.1](#) or those toxicities listed in Section [3.3](#) that require treatment to be stopped
- More than 6 weeks has elapsed since the patient received protocol therapy
- Subject's request to withdraw from protocol therapy
- Investigator's decision to withdraw the patient
- Subject's non-compliance with trial treatment or procedure requirements that requires removal in the opinion of the PI
- Pregnancy
- The drug manufacturer can no longer prove the study agent
- Study is cancelled for any reason

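### The liver-test continuation sentence in Section 3.1.1.2 uses *or* where *and* is needed, so read literally it keeps dosing two kinds of patient whom Section 3.1 takes off treatment

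*Combined protocol and SAP*

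**What the plan says.** The liver-test bullet in Section 3.1.1.2 does two jobs.

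- **It defines an exception to the DLT rule.** The event must be a "Non-sustained (< 7 days) grade 3 liver function test" abnormality and, after the tests are named, the bullet limits this to "abnormalities deemed unrelated or unlikely related to avelumab, in the absence of clinical signs of hepatic dysfunction". All of these conditions must hold. For patients who enter with Grade 1 elevations, an increase of at least 10 times "baseline will be considered dose-limiting and these patients will be closely monitored for liver function abnormalities".
- **It tells staff when to keep dosing.** Both drugs go on "as long as these abnormalities do not persist for more than 7 days or the patient does not exhibit findings consistent with hepatic toxicity".

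Three other places say when dosing ends.

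- Section 3.1: "Treatment will continue for a maximum of 6 cycles or until toxicity (i.e., dose limiting toxicity as found in Section 3.1.1", or a toxicity requiring a hold under Section 3.3.
- Closing paragraph of Section 3.1.1.2: "Occurrence of any DLT-defining toxicity after the first 28 days of treatment will lead to permanent discontinuation of protocol therapy".
- Section 3.8.1 gives, among the grounds for removal from therapy, "Unacceptable toxicities as listed in Section" 3.1.1.

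The bullet is followed by a pointer: "Management and dose modifications associated with the above adverse events are outlined in Section 3.3".

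**The concern.** The exception and the dosing instruction sit in one bullet and should be mirror images: a patient who no longer qualifies for the exception should no longer be dosed. They are not. The exception fails if either the duration or the signs condition fails. The dosing instruction ends treatment only if both fail. Staff facing a patient with, say, confusion on the third day of a Grade 3 rise have one sentence telling them to carry on and another section telling them to stop.

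This matters most in real time. At onset nobody knows how long a rise will last, so the continuation sentence is the one that staff act on. The event is also foreseeable. Section 1.2.7 reports persistent, dose-limiting Grade 3 ALT and AST rises on bolus rhIL-15. Section 1.2.8.2 reports hepatotoxicity as one of two DLTs at 4.0 mcg/kg/day by continuous infusion, the same daily dose as Level 4 here, though given for 10 days and not 5.

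**Working it through.** **Does the plan's own figure move?** The design figure that depends on DLT scoring is the escalation table in Section 10.2. With true DLT rate p, the chance of escalating is (1−p)³ + 3p(1−p)² × (1−p)³. At p = 0.5 this is 0.125 + 0.375 × 0.125 = 0.172. At 10%, 20%, 30%, 40% and 60% it is 0.906, 0.709, 0.494, 0.309 and 0.082. All six agree with the table. The input is whether a patient had a DLT. The exception decides that, and the continuation sentence does not, so nothing here changes.

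**The logic.** Take a Grade 3 rise that is at least possibly related to rhIL-15 (otherwise Section 3.1.1 does not make it a DLT) and unrelated or unlikely related to avelumab. Leave aside the 10-times-baseline group. Then:

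- Excepted = (under 7 days) and (no signs).
- Continue, as written = (not more than 7 days) or (no signs).
- Continue, with *and* only = (not more than 7 days) and (no signs).
- Continue, with *and* and the same limit as the exception = (under 7 days) and (no signs).

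A conflict is a patient who is not excepted, hence a DLT, but who continues.

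| Duration (days) | Signs | Excepted | As written | *and* only | *and*, under 7 days |
|---|---|---|---|---|---|
| 3 | no | yes | continue | continue | continue |
| 3 | yes | no | continue: conflict | stop | stop |
| 6.9 | no | yes | continue | continue | continue |
| 6.9 | yes | no | continue: conflict | stop | stop |
| 7 | no | no | continue: conflict | continue: conflict | stop |
| 7 | yes | no | continue: conflict | stop | stop |
| 10 | no | no | continue: conflict | stop | stop |
| 10 | yes | no | stop | stop | stop |

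Conflicts fall from 5 of the 8 cells to 1 and then 0. These are cells in a grid, not proportions of patients. An excepted patient continues under every version.

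**When each case would bite.** For a rise starting on Days 1 to 5 of a cycle, its age at the Day 8 avelumab dose is 8 minus the onset day, so 7, 6, 5, 4 or 3 days. At the Day 22 dose it is 22 minus the onset day, so 21 down to 17 days. The rhIL-15 infusion ends about 120 hours after it starts (Section 3.3.1), before such a rise can reach 7 days. The signs case can therefore arise during the infusion itself. The long-duration case concerns avelumab on Day 8 (Day 1 onset only), avelumab on Day 22, and the next cycle, and only if the rise has not resolved.

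**Does Section 3.3 settle it?** Not clearly. Section 3.3.1 has no hepatic stopping rule for rhIL-15, and it allows infusion while laboratory abnormalities listed in Section 3.1.1 are corrected. Table 9 permanently discontinues therapy for AST or ALT above 5 times ULN, but it is headed as covering immune-related events, while this exception is for rises not attributed to avelumab.

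**The neighbouring rule.** For asymptomatic lymphocytopenia and for Grade 3 neutropenia, Section 3.1.1.1 continues the drugs unless there are clinical signs of significant infection. There, signs alone are enough to override continuation. Only the liver sentence lets short duration outweigh signs.

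**The case against.** **The reference is only to excepted rises.** The bullet sits under a heading about exceptions, so the continuation sentence could be read as covering only rises that still qualify, and the sponsor probably meant that neither bad feature may be present. The intention is likely. But on that reading the two conditions in the sentence would be redundant, and as worded either one is enough to continue.

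**Section 3.8.1 is not decisive.** Its phrase about toxicities that require treatment to be stopped may qualify only those in Section 3.3. That is fair, but Section 3.1 and the after-day-28 rule carry the conflict without it.

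**Other rules point toward stopping.** Section 12.4 says that the avelumab manufacturer's discontinuation recommendations are followed for Grade 3-4 LFT elevations, with no limit to immune-related ones. Section 3.3 says that holding one agent means holding the other. This stands, and it cuts both ways. These rules make it less likely that a patient would in fact be dosed, but applied to every Grade 3 rise they would cancel the continuation sentence altogether, even for a patient who meets the exception. They are a further competing instruction that any amendment has to address.

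**The 10-times-baseline group.** A reader might infer a third kind of conflict, because the continuation sentence does not mention this group. The documents do not support that: the clause just before it already calls such an increase dose-limiting, and not repeating a rule is not contradicting it.

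**Small exposure for long rises.** Section 12.4 reports that LFT elevations in the continuous-infusion trial occurred only during infusion, so the long-duration case is probably the less common one. This also stands.

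**Conclusion.** The sentence is wrong as written and should be corrected. Taken literally, it continues both drugs in a patient with hepatic signs whose rise has not passed 7 days, mainly one in its first days, and in a sign-free patient whose rise lasts 7 days or more. Both have lost the exception, and Section 3.1 stops treatment for both (the closing paragraph of Section 3.1.1.2 does so after day 28). This rests on the literal reading, and on the event being at least possibly related to rhIL-15 and not attributed to avelumab.

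Three stronger conclusions are tempting and not supported.

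- **That the MTD is biased.** DLT scoring follows the exception, so the DLT count, the MTD and the escalation table are unchanged.
- **That half of patients are at risk.** Section 1.2.7 reports 2 of 4 patients with persistent Grade 3 ALT and AST rises at 1.0 mcg/kg/day, but on bolus dosing, whose toxicity Section 1.2.8 ascribes to very high peak levels. The 4.0 mcg/kg/day hepatotoxicity followed 10 days of infusion (4.0 × 10 = 40 mcg/kg) and not 5 (4.0 × 5 = 20 mcg/kg). These show that the event can happen, not how often it will here. The documents give no frequency for 5-day rhIL-15 with avelumab.
- **That changing one word settles everything.** It leaves the exactly-7-day case, and it leaves Section 12.4 and Table 9 unreconciled.

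**What to change.** Replace the continuation sentence in Section 3.1.1.2 with wording to this effect:

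> Both rhIL-15 and avelumab continue only while the abnormality has lasted less than 7 days and the patient has no findings of hepatic toxicity; otherwise protocol therapy is stopped under Sections 3.1 and 3.8.1.

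In the same amendment, state that the Grade 3-4 liver-test discontinuation rule in Section 12.4 and Table 9 takes precedence for any elevation at least possibly related to avelumab, and that only elevations meeting the Section 3.1.1.2 exception may continue. Repeating the 10-times-baseline rule in the new sentence is optional, for clarity.

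The cost is one replaced sentence and one clarifying statement, with no new data or visits. The downside is that an occasional patient stops earlier than the literal *or* would allow.

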3.3 DOSE MODIFICATIONS

If one study agent is held, the other must be held as well. The maximum time agents may be held cannot exceed 6 weeks. Patients who exceed 6 weeks must be removed from the study (section 3.7).

3.3.1 rhIL-15-specific Adverse Events

Please refer to the Comprehensive Adverse Event and Potential Risk list (CAEPR) for rhIL-15 presented in Section 14.1.2.

Dose of rhIL-15 is based on the dose level and patient's weight at the beginning of each cycle and can only be modified for rounding and/or consistency with prior cycles, and not for adverse events or renal/hepatic dysfunction. Infusion may continue during correction of electrolyte and other laboratory abnormalities listed in Section 3.1.1. Infusion may be interrupted for up to two hours each day, but treatment should end 120 (± 1) hours after initiation on Day 1.

Note: IL-15 should not be administered within 1 week of steroid administration when steroids are given to treat avelumab toxicities as listed in the Section 3.3.2.

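### The stop rule for related Grade 3 or higher toxicity conflicts with hold-and-resume steps for some immune-related events, most plainly Grade 3–4 thyroid disorders and type I diabetes in Table 12

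*Combined protocol and SAP*

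**What the plan says.** **Stop rule.** Section 3.1.1 defines a dose-limiting toxicity (DLT) as a related Grade 3, 4 or 5 toxicity in the first 28 days. The exceptions are low lymphocyte or neutrophil counts without infection, leukocytosis, brief electrolyte or albumin changes, and short liver-test rises not attributed to avelumab. Three places then end therapy:

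- 3.1.1.2, closing paragraph: "Occurrence of any DLT-defining toxicity after the first 28 days of treatment will lead to permanent discontinuation of protocol therapy". These later events do not count for escalation.
- 3.1: treatment runs until progression, six cycles or toxicity, the last explained as "dose limiting toxicity as found in Section 3.1.1 or toxicity requiring hold as defined in Section 3.3".
- 3.8.1: removal for "Unacceptable toxicities as listed in Section" 3.1.1, or for those in 3.3 "that require treatment to be stopped".

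**Resume rule.** In 3.3.2.2, Tables 6, 10, 12 and 13 withhold avelumab for certain events of Grade 3 (Table 12: Grade 3 or 4) and restart it after improvement.

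**Limits on a hold.** Section 3.3 says "If one study agent is held, the other must be held as well" and "The maximum time agents may be held cannot exceed 6 weeks". Section 3.8.1 removes a patient when "More than 6 weeks has elapsed since the patient received protocol therapy". Section 3.3.1 adds that "IL-15 should not be administered within 1 week of steroid administration when steroids are given to treat avelumab toxicities".

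**The concern.** A related Grade 3 immune event meets the DLT definition, because no exception in 3.1.1.1 or 3.1.1.2 reaches it. The removal clauses then say stop for good, while some of the tables say pause and restart. Since both agents are held together and ending protocol therapy ends avelumab, the two instructions cannot both be followed. At stake is whether a patient is re-exposed after a serious immune event, in a trial whose primary objective is safety and toxicity. Two patients with the same event could be handled differently, and either choice would breach one section.

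The wording of 3.1 raises a second problem. It treats the need for a hold as the end of treatment, while 3.3 provides for holds and later restarts.

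**Working it through.** The plan gives no figure on this point, so the check is a comparison of text plus a day count.

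**1. Immune-event tables against the stop rule (3.3.2.2)**

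| Table | Event | Instruction | Against the stop rule |
|---|---|---|---|
| 6, gastrointestinal | first Grade 3 | withhold, restart after taper | conflicts |
| 7, skin | Grade 3 | withhold, no restart step given | conflict implied only |
| 8, lung; 9, liver | Grade 3–4 | end protocol therapy | agree |
| 10, renal | Grade 3 (row covers 2–3) | withhold, restart after taper | conflicts |
| 11, cardiac | not graded | restart only if an immune cause is ruled out | not comparable |
| 12, endocrine | Grade 3–4 thyroid, adrenal, type I diabetes | withhold, restart at Grade 1 or less, no taper stated | conflicts |
| 12, hypophysitis | severe or life-threatening | withhold, steroids with taper, restart on improvement | conflicts |
| 13, other | first Grade 3 | withhold, restart after taper | conflicts |

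Of 8 tables, 4 conflict explicitly, 1 by implication, 2 agree and 1 is not graded. Tables 6, 10 and 13 stop at Grade 4, so only Table 12 restarts after a Grade 4 or life-threatening event.

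**2. Linking text.** Section 3.1.1.2 points to 3.3 for management. Section 3.4 points to 3.8.1 for reasons to end treatment. Section 12.4 says the manufacturer's advice on discontinuing avelumab will be followed. None of these ranks one rule over the other.

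**3. What the 6-week limit leaves**

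Inputs: limit 6 × 7 = 42 days (3.3, 3.8.1); taper of at least 1 month, taken as 28 to 31 days (Tables 6, 10, 13 and the hypophysitis row); 7 steroid-free days before IL-15 (3.3.1).

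Days left = 42 − taper − steroid gap:

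- avelumab next: 42 − 31 = 11 to 42 − 28 = 14 days;
- IL-15 next: 11 − 7 = 4 to 14 − 7 = 7 days. Section 4 asks for more than 7 days, so this is slightly generous.

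Section 3.8.1 counts from the last treatment, not from the start of the hold, so these days must cover onset as well as recovery to Grade 1 or less. If onset is 7 to 14 days after the last dose (an assumption; the documents give no figure), then with avelumab next:

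- onset at day 7: 42 − 7 − 31 = 4 to 42 − 7 − 28 = 7 days;
- onset at day 14: 42 − 14 − 31 = −3 to 42 − 14 − 28 = 0 days.

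With IL-15 next, 7 days fewer remain: −10 to 0 across the same range. Restarting after a taper is therefore nearly closed off.

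In the Table 12 Grade 3–4 row, thyroid disorders and type I diabetes are managed with hormone, anti-thyroid drug or insulin, without steroids. Up to 42 days remain, or 42 − 14 = 28 to 42 − 7 = 35 under the same onset assumption. Here both instructions can apply to the same patient.

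**4. The hold wording in 3.1.** Grade 2 rows in Tables 6, 8, 9, 10 and 13 withhold avelumab and then restart it. Read literally, 3.1 ends treatment for each of them. Section 3.8.1 names only those 3.3 toxicities that call for stopping, so 3.1 and 3.8.1 also differ from each other.

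**5. MTD.** Qualifying events in the first 28 days count as DLTs whether the patient later stops or restarts, and later events never count. The escalation probabilities in 10.2 do not depend on this point. For example, at a true DLT rate p = 0.5, (1 − p)³ + 3p(1 − p)² × (1 − p)³ = 0.125 + 0.375 × 0.125 = 0.172, matching the stated 0.17.

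**The case against.** The strongest reply is that a workable default already exists. In 3.8.1 the toxicity triggers are alternatives, so meeting 3.1.1 is enough for removal, and 3.1 and 3.1.1.2 point the same way. A cautious investigator would stop. That stands, and it is why the main fix below adopts this default. It does not remove the conflict, because it leaves the Grade 3 restart steps without effect. It also makes the separate stops for recurrent Grade 3 events in Tables 6 and 13 redundant. Tables 8 and 9 show that where the tables mean to end all therapy they say so.

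The 6-week limit is a second reply, and it largely succeeds for Tables 6, 10 and 13 and for hypophysitis treated with steroids. It does not reach thyroid disorders or type I diabetes.

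Third, 3.1 is a design overview, and reading it to end therapy at every Grade 2 hold would empty much of 3.3. That is fair. The defect is loose wording, and it needs only a short correction.

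A reader might also infer three stronger things that the documents do not support:

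- *That four tables are in equal practical conflict.* The day count shows one clearly live row.
- *That sites would diverge.* The trial is single-center, and under 7.4.1 the team discusses each patient at least weekly. The remaining risk is inconsistency between patients.
- *That the MTD is compromised.* DLT counting is the same under either rule.

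**Conclusion.** The inconsistency is real and should be fixed, but it is narrow. Four of the eight immune-event tables contradict the stop rule in words. In practice the contradiction is plain for a related Grade 3–4 thyroid disorder or type I diabetes that improves to Grade 1 or less within 6 weeks of the last treatment: one set of clauses ends therapy and another restarts it. In Tables 6, 10 and 13 it appears only with very rapid recovery; otherwise both routes end in removal. The hold wording in 3.1 is a separate, simpler error.

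Few patients are likely to be involved: accrual is capped at 30, and the event must be severe, related and quickly controlled. The number cannot be estimated, because the avelumab risk list in 14.2.2 gives frequency bands without Grade 3 rates. MTD determination and sample size are unaffected.

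The textual finding needs no assumption. The day counts take 1 month as 28 to 31 days, and the tighter range assumes onset 7 to 14 days after the last dose.

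**What to change.** 1. In 3.1, replace the phrase about toxicity requiring a hold with *toxicity requiring permanent discontinuation*, in line with 3.8.1.
2. In 3.3.2.2, state that the stop rule in 3.1.1.2 and 3.8.1 overrides the restart steps for related events of Grade 3 or higher, so that those steps apply only to lower grades. The removal clauses already set this default.

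If the sponsor prefers to keep re-treatment for endocrine events controlled by hormone replacement, anti-thyroid drugs or insulin, add that single exception to 3.1, 3.1.1.2 and 3.8.1, limited to events after day 28 and within the 6-week limit. This is a clinical decision with a safety consequence, because it permits re-exposure that the removal clauses now bar.

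Under either choice, qualifying events in the first 28 days remain DLTs.

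The cost is a protocol amendment with IRB approval, with no change to sample size, visits or data collection. Under the default, a few patients with manageable endocrine events would stop therapy.

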3.1.2 Dose Escalation

Dose escalation will proceed according to the following schedule (**Table 2**). Dose escalation will follow the following guidelines (**Table 3: Dose Escalation**). DLT is defined above. Dose-limiting toxicity (DLT) is defined above. Each patient will continue treatment at the dose level they were enrolled – there will be no intra-patient dose escalation.

The MTD is the dose level at which no more than 1 of up to 6 patients experience DLT during the DLT evaluation window(s), or the dose below that at which at least 2 (of ≤ 6) patients have DLT. The protocol will be amended to note the MTD once determined.

Table 2: IL-15 Dose Escalation Schedule

Dose Level	rhIL-15 (mcg/kg)	Avelumab (mg/kg)
Level 1	1	10
Level 2	2	10
Level 3	3	10
Level 4	4	10

*Doses are stated as exact dose in units (e.g., mg/m², mcg/kg, etc.) rather than as a percentage.

Table 3: Dose Escalation Guidelines

Number of Patients with DLT at a Given Dose Level	Escalation Decision Rule
0 out of 3	Enter 3 patients at the next dose level.

Number of Patients with DLT at a Given Dose Level	Escalation Decision Rule
≥2	Dose escalation will be stopped. This dose level will be declared the maximally administered dose (highest dose administered). Three (3) additional patients will be entered at the next lowest dose level if only 3 patients were treated previously at that dose.
1 out of 3	Enter at least 3 more patients at this dose level. 
• If 0 of these 3 patients experience DLT, proceed to the next dose level.• If 1 or more of this group suffer DLT, then dose escalation is stopped, and this dose is declared the maximally administered dose. Three (3) additional patients will be entered at the next lowest dose level if only 3 patients were treated previously at that dose.
≤1 out of 6 at highest dose level below the maximally administered dose	This is generally the recommended phase 2 dose. At least 6 patients must be entered at the recommended phase 2 dose.

